### ***14.9.1. Study-wide termination or suspension***

Possible reasons for considering study suspension or termination of the study for all centers include but are not limited to:

- AEs and device deficiencies associated with the system or product under investigation which might endanger the safety or welfare of subjects
- Observed/suspected performance different from the product's design intent
- Decision by Medtronic or regulatory body (medically/ethically justifiable) where the study is operating under regulatory body authority

### ***14.9.2. Investigator/ study site termination or suspension***

Possible reasons for clinical investigator or center termination or suspension include but are not limited to:

- Failure to obtain initial EC/IRB approval or annual renewal of the study
- Consistent non-compliance to the CIP (e.g., failure to adhere to inclusion/exclusion criteria, failure to follow subjects per scheduled follow ups, etc.)
- Lack of enrollment
- Noncompliance to regulations and the terms of the clinical trial agreement (e.g., failure to submit data in a timely manner, failure to follow up on data queries and monitoring findings in a timely manner, etc.)
- EC/IRB suspension of the center
- Fraud or fraudulent misconduct (as defined by local law and regulations)
- Investigator request (e.g., no longer able to support the study)

### ***14.9.3. Procedures for planned study closure, termination, or suspension***

#### ***14.9.3.1. Medtronic-initiated***

Medtronic will promptly inform the clinical investigators of the reasons for a study termination or suspension and inform the regulatory authority(ies) (where required per regulatory requirements).

- In the case of study termination or suspension for reasons other than a temporary EC/IRB approval lapse, the investigator will promptly inform the EC/IRB.
- In the case of study termination, the investigator must inform the subjects and may inform the personal physician of the subjects to ensure appropriate care and follow up is provided.
- In the case of a study suspension, subject enrollment must stop until the suspension is lifted by Medtronic. Subjects already enrolled should continue to be followed out of consideration of their safety, rights, and welfare.

#### ***14.9.3.2. Investigator-initiated***

The investigator will promptly inform:

- Medtronic and provide a detailed written explanation of the termination or suspension.
- The institution (where required per regulatory requirements).
- The EC/IRB.
- The subjects and may inform the personal physicians of the subjects to ensure appropriate care and follow up is provided.

In the case of a study suspension:

- Subject enrollment must stop until the suspension is lifted.
- Subjects already enrolled should continue to be followed out of consideration of their safety, rights, and welfare.

#### ***14.9.3.3. Ethics Committee/ Institutional Review Board initiated***

The investigator will promptly inform:

- Medtronic and provide a detailed written explanation of the termination or suspension within five business days.
- The institution (where required per regulatory requirements).
- The subjects and may inform the personal physicians of the subjects, with the rationale for the study termination or suspension.

In the case of a study suspension:

- Subject enrollment must stop until the EC/IRB suspension is lifted.
- Subjects already enrolled should continue to be followed in accordance with EC/IRB policy or its determination that an overriding safety concern or ethical issue is involved.

### **14.10. Role of Sponsor Representatives**

As the sponsor of this clinical study, Medtronic has the overall responsibility for the conduct of the study, including assurance that the study will be conducted according to international guidelines including latest version of ISO 14155 and local laws. In this study, Medtronic will have certain direct responsibilities and may delegate other responsibilities to consultants and/or contract research organizations.

The principles of the Declaration of Helsinki have all been implemented in this study by means of the Patient Information and Informed Consent process, EC/IRB approval, study training, clinical trial registration, preclinical testing, risk benefit assessment, publication policy, etc.

Medtronic's general duties consist of submitting applications and information to appropriate regulatory authorities, obtaining EC/IRB approvals prior to allowing shipment of devices, selecting qualified investigators, ensuring proper clinical site monitoring, ensuring subject informed consent is obtained and ensuring that the EC/IRB and relevant regulatory authorities are promptly notified of significant new information about the investigation.

Medtronic is responsible for providing quality data that satisfies regulations and informing investigators, EC/IRB, and relevant regulatory authorities of UADEs/SADEs and deviations from the investigational plan as appropriate. The Medtronic clinical study team will provide written progress reports and a final report.

Sponsor representatives may provide support at the study site as required for the study under supervision of the principal investigator, including:

- Provide study training relevant and pertinent to the involvement of personnel conducting study activities and investigator responsibilities
- Technical support at RDN procedure under the supervision of a study investigator, but no data entry, shall be performed by Medtronic personnel or their representatives at study sites
- Monitoring and auditing activities
- In addition, for this study, sponsor representatives may be authorized by the principal investigator to perform the following significant study related duties:
  - Support study investigators in performing the study procedure
  - Support data collection during the procedure and device testing

Support data collection during the study follow-up visits.

#### **14.11. Site Selection**

The role of the principal investigator is to implement and manage the day-to-day conduct of the clinical study as well as ensure data integrity and the rights, safety and well-being of the subjects involved in the clinical study.

An investigational site may be selected for participation in the clinical study if compliant with the following requirements:

- Investigator has previous experience with the Symplicity Spyral renal denervation system.
- Investigator should have adequate staff that is accessible and has time to manage the study.
- Investigator should have adequate staff to perform blood pressure measurements.
- Investigator, and sub-investigators (if applicable) and all key site staff must be willing to provide his/her curriculum vitae.
- Investigational site must be willing to comply with the CIP and data collection requirements, including timely reporting of adverse events and device deficiencies as required by the CIP.
- Investigational site has demonstrated experience with conducting clinical (device) studies that comply with applicable regulatory standards.

- Investigational site is willing to participate in follow-up of subjects for a minimum of 12 months (and up to a maximum of 5 years).
- Investigational site has an internet connection with sufficient speed of data transfer.
- Investigational site agrees to one RDN operator per site unless an exception is granted in writing by the sponsor.

A list of participating investigational sites and IRBs, including contact information, and investigators (with titles), will be available as a separate document.

#### **14.12. Site Activation**

Prior to investigational site activation or subsequent involvement in clinical study activities, Medtronic will provide clinical study training relevant to the involvement of personnel conducting clinical study activities. Medtronic will train site personnel on, but not limited to, the CIP, relevant standards and regulations, informed consent, written clinical investigation agreements, data collection and reporting tools, investigator responsibilities, as well as device/product training. Study specific training will be documented prior to investigational site activation.

Training will occur prior to site activation at each site, and will include at a minimum the following topics (as applicable to the role at the site):

- Technical overview of device(s)
- Procedural training for proceduralist
- CIP overview and study procedures
- Investigational device disposition and accountability procedures
- Procedures for returning unused/explanted devices
- CRF completion and management, including electronic data entry
- Investigator and sponsor responsibilities
- Procedures for obtaining informed consent
- EC/IRB requirements
- Adverse event/device deficiency reporting procedures and timelines
- Deviation reporting procedures
- Monitoring requirements and expectations
- Potential regulatory inspections and audits by the sponsor or sponsor representative
- Site record maintenance and retention
- Regulatory requirements for commercially approved devices in a clinical study, including timely adverse event and complaint reporting
- Any additional regulatory requirements

The sponsor will supply all required study materials for appropriate data collection before study start. Data collected on each subject will be recorded on a web-based electronic CRF. The passwords for the electronic CRF will only be distributed to investigational centers where the sponsor has written documentation of site readiness.

Investigational sites will receive a formal letter of site activation, upon receipt of or completion of the following:

- Curriculum vitae of the principal and sub-investigators and all key site staff
- A signed trial agreement.
- Financial disclosure from the investigators
- Competent Authority approval (as applicable to the geography)
- A copy of the EC/IRB approval letter, along with the voting roster
- The EC/IRB approved subject information and informed consent form
- Documented training (at least CIP, CRF, EDC, ICF process and product training ( as applicable to their role)) of the investigative team
- Lab certificate and lab normal values/ranges
- Delegated task list
- Confirmation of calibration and maintenance of equipment and maintenance of facilities

- Confirmation of adequacy of equipment/facilities (e.g., a quiet room to perform the blood pressure measurements)

Medtronic will control the supply of study materials and will only grant site activation when above activation criteria are met, and the site receives a formal activation letter from Medtronic.

#### ***14.12.1. Curriculum Vitae***

Prior to study start, a current signed and dated curriculum vitae from the principal investigator, all sub-investigators and all key site staff participating in this clinical study as listed on the delegated task list shall be obtained, evidencing the required qualifications, including the year, and where obtained, and including their current position at the investigational site. The signature on the CV must be dated within three years prior to the date of activation of the investigational site.

#### ***14.12.2. Clinical Trial Agreement***

Medtronic contracts with participating institutions/investigators through a clinical trial agreement that defines the scope and responsibilities and associated compensation related to carrying out the obligations under a clinical study sponsored by Medtronic. A clinical trial agreement shall be in place, signed by the participating investigational site and/or principal investigator of each investigational site, as per the local legal requirements, and returned to Medtronic prior to the commencement of any clinical study activities. The investigator is indicating approval of the CIP and subsequent amendments, by a fully executed agreement. Amendments to the CIP shall be agreed upon between Medtronic and investigator(s) and be recorded with a justification for the amendments.

### **16.1.3. *List of participating investigational sites and investigators***

A list of investigational sites, IRBs and investigators will be provided under a separate cover.

### **16.2. Case Report Forms**

A copy of the CRFs will be provided under a separate cover.

### **16.3. Sample Investigator Agreement**

A sample investigator agreement will be provided under a separate cover.

### **16.4. Event Definitions**

**All-cause mortality:** Death irrespective of cause.

**Cardiovascular death:** Any death due to immediate cardiac or vascular cause (e.g., sudden cardiac death, AMI, stroke, heart failure, fatal arrhythmia, or any procedure-related death).

**Hospitalization for hypertensive crisis:** Severely elevated blood pressure (BP), usually higher than 180/110 mm Hg, together with progressive or impending target organ damage, requiring in-patient

hospitalization and typically admission to the intensive care unit (ICU) (e.g., with parenteral [IV] antihypertensive medications), not related to confirmed nonadherence with medication or the protocol.

**Non-cardiovascular death:** Any death not covered by the above definition for cardiovascular death, including death due to infection, sepsis, pulmonary causes, accident, suicide, or trauma.

**End-stage renal disease (ESRD):** Two or more eGFR measurements <15 mL/min/m^2 at least 21 days apart and requiring dialysis for one or more of the following:

- Volume management refractory to diuretics
- Hyperkalemia unmanageable by diet and diuretics
- Acidosis bicarbonate <18 unmanageable with HCO3 supplements
- Symptoms of uremia, nausea, vomiting

**Major adverse events (MAE),** defined as a composite of the following events:

- All-cause mortality
- ESRD
- Significant embolic event resulting in end-organ damage (e.g., kidney/bowel infarct, lower extremity ulceration or gangrene, or doubling of serum creatinine documented by at least two measurements at least 21 days apart)
- Renal artery perforation requiring reintervention
- Renal artery dissection requiring intervention
- Vascular complications
- Hospitalization for hypertensive crisis not related to confirmed non-adherence with medications
- New renal artery stenosis > 70%, confirmed by angiography by the angiographic core lab

**Major bleeding according to TIMI definition:** Intracranial hemorrhage; ≥5g/dl decrease in hemoglobin concentration, a ≥15% absolute decrease in hematocrit, or death due to bleeding within seven days of the procedure)

**Myocardial infarction (MI):** MI is defined as the concurrent documentation of two of the three elements listed below in the appropriate clinical circumstance:

1. Chest pain or ischemic equivalent
2. New pathologic q waves in at least 2 contiguous ECG leads
3. Cardiac biomarker elevation by any of the definitions below:

Appropriate cardiac enzyme data (respecting top-down hierarchy):

a) CK greater than or equal to 2\* URL confirmed by:

- CKMB > 1\*URL or
- in the absence of CKMB: Troponin > 1\*URL or

b) in the absence of CK:

- CKMB > 3\*URL
- In the absence of CK and CKMB: Troponin > 3\*URL
- In the absence of CK, CKMB and Troponin, clinical decision based upon clinical scenario

**New renal artery stenosis:** Greater than 70% renal artery stenosis confirmed by analysis of angiography by the core lab. If core lab analyses are unavailable, site reported analysis may be used. The date of the event will be the date of confirmatory angiography.

**Renal artery dissection:** Creation of a false lumen between the layers of the artery requiring intervention.

**Renal artery perforation:** Puncture creating a hole in the vessel wall requiring intervention.

**Renal artery reintervention:** Interventional procedure performed on the renal artery following completion of the renal denervation procedure and removal of the guide catheter.

**Significant embolic event:** Sudden obstruction of a blood vessel by debris (i.e., blood clot, plaques, fat, bacterial mass, cancer cells, or air bubbles) resulting in end-organ damage. Examples include:

- Kidney/bowel Infarct: necrosis (cell death) of an area of tissue in all or part of the organ due to cessation of the blood supply due to stenosis or occlusion
- Lower extremity ulceration: a non-healing lesion on a body surface (i.e., skin, mucous membrane)
- Gangrene: necrosis of tissue usually resulting from deficient or absent blood supply
- Doubling of serum creatinine confirmed by at least two measurements over 21 days apart
- DOES NOT INCLUDE MI OR STROKE WHICH ARE ADJUDICATED SEPARATELY

**Stroke:** Sudden onset of vertigo, numbness, dysphasia, weakness, visual field defects, dysarthria, or other focal neurological deficits due to vascular defects in the brain such as hemorrhage, embolism, thrombosis, or rupturing aneurysm, that persists more than 24 hours.

**Vascular Complications:** Complications that require surgical repair, interventional procedure (not including manual compression), thrombin injection, or blood transfusion (requiring more than 2 units of packed red blood cells within any 24-hour period during the first 7 days post-procedure); possible vascular complications are as follows:

- Clinically significant groin hematoma: swelling due to the accumulation of blood around an organ, tissue or space caused by the leakage of blood from a vessel
- Arteriovenous fistula: formation of an abnormal connection between an artery and a vein
- Pseudoaneurysm: a hematoma that forms as the result of a leaking hole in an artery. Note that the hematoma forms outside the arterial wall, so it is contained by the surrounding tissues. Also, it must continue to communicate with the artery to be considered a pseudoaneurysm
- Excessive Bleeding: requires >2 units of packed red blood cells (PCRB) within any 24-hour period during the first 7 days post-randomization and documented bleeding

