### ***9.1.8. Confirmatory Blood Draws to Assess Renal Function***

Serum creatinine values will be assessed throughout the study. A second blood draw will be required to confirm a sustained change in renal function in the event of one of the following:

- >50% increase in serum creatinine from baseline (Screening Visit 2)
- eGFR <15 mL/min/1.73m^2 using the 4 variable MDRD calculation

The additional blood draw must be taken at least 21 days from the date of the event noted above and documented on an Unscheduled Follow-up CRF. In the event the second blood draw results in the same event (e.g., >50% increase in serum creatinine from baseline), an adverse event must be reported. If the event is a continuation of an already-identified sustained elevation that did not return to <50% of baseline value, another blood draw is not necessary.

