All the safety endpoints except "Increase in serum creatinine $>50\%$ from SV2" will be adjudicated by the Clinical Events Committee (CEC). The following algorithm will be used to evaluate the safety event rates: The denominator will include all subjects who either had a CEC adjudicated event prior to the time of interest (180 days for 6 months events, for example), or had last contact date that is beyond the lower window of the follow up (166 days for 6 month events, for example). The numerator will include all subjects who had CEC adjudicated events up to the time of interest (180 days for 6 months events, for example).

The safety endpoints will be summarized using counts and percentages, and no comparison group will be used for the safety analysis. These analyses will be performed for the ITT population defined in 7.1.3.1.

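### The stroke definition has no alternative for death within 24 hours, so a rapidly fatal stroke would be missing from the stroke safety rate

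*Protocol*

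**What the plan says.** Stroke is listed as a safety endpoint in Protocol 4.2.2 and SAP 7.7.1. Its only definition is in Protocol 16.4, which describes a sudden focal deficit of vascular cause and ends with the condition "or rupturing aneurysm, that persists more than 24 hours". The SAP does not redefine it.

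The counting rule is in SAP 7.7.1: "The numerator will include all subjects who had CEC adjudicated events up to the time of interest". The denominator takes subjects with an adjudicated event before the time point, or with a last contact beyond the lower edge of the visit window.

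Three other parts of the protocol bear on the point:

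- **Death.** In 16.4 all-cause mortality is "Death irrespective of cause". Cardiovascular death gives stroke as one of its causes ("e.g., sudden cardiac death, AMI, stroke, heart failure, fatal arrhythmia, or any procedure-related death").
- **ESRD.** Section 16.4 asks for two or more eGFR values below 15 "at least 21 days apart and requiring dialysis for one or more of the following". Section 9.1.8 sets the matching sampling rule: "The additional blood draw must be taken at least 21 days from the date of the event noted above".
- **Creatinine doubling.** It appears twice in 16.4 as an example of an embolic event. The major adverse event list has "doubling of serum creatinine documented by at least two measurements at least 21 days apart", and the embolic-event definition has "Doubling of serum creatinine confirmed by at least two measurements over 21 days apart".

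**The concern.** A persistence test separates stroke from transient deficits in subjects who survive. It cannot be met by a subject who dies first. Applied literally, it removes from the stroke endpoint the strokes that kill fastest.

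Protocol 10.1 names stroke among the risks of being off antihypertensive drugs, and subjects stay off them through the 3-month visit. Safety is reported as counts and percentages with no comparator, so a single unclassified event changes the reported stroke rate. If the rule is not settled beforehand, the CEC would have to choose between the written definition and clinical sense after seeing the case.

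**Working it through.** The plan states no figure that depends on this definition, so there is none to reproduce. The check is a reading of the conditions, followed by simple arithmetic.

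**1. A stroke fatal at 12 hours, taken through each endpoint as written**

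| Endpoint | Counted? | Reason |
|---|---|---|
| Stroke | No | The deficit did not last beyond 24 hours; no death alternative |
| Significant embolic event | No | The definition sends stroke to separate adjudication |
| All-cause mortality, hence the composite | Yes | Any death counts |
| TIMI major bleeding | Only if hemorrhagic | Intracranial hemorrhage is listed |

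The composite is counted per subject, and this subject is already in it through death. Only the stroke rate changes.

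**2. Neighbouring definitions**

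Other endpoint definitions in 16.4 provide for awkward cases. Myocardial infarction falls back on clinical judgement when no biomarkers exist. New renal artery stenosis may use the site reading if the core laboratory has none. TIMI bleeding names death due to bleeding. Stroke has no comparable clause, which suggests a drafting gap and not a deliberate choice.

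**3. Size**

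Assumptions: 50 evaluable treated subjects (Protocol 5 says approximately 50) and one stroke fatal within 24 hours. The intervals are exact (Clopper-Pearson) 95% intervals, added for illustration; the plan does not call for them.

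- As written: 0/50 = 0% (0 to 7.1%).
- As written, if the denominator is read endpoint by endpoint, so that a subject who died early without an adjudicated stroke leaves it too: 0/49 = 0% (0 to 7.3%).
- With the death alternative: 1/50 = 2.0% (0.05 to 10.6%).

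**4. How likely**

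Protocol 3.1 reports one new stroke by three months among 166 + 165 = 331 randomised SPYRAL HTN-OFF MED subjects. At that rate, 50 subjects would have 50 × 1/331 = 0.15 strokes of any kind by three months. Strokes fatal within a day would be some fraction of that. A rate based on one event is very imprecise, but such an event is clearly unlikely.

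**5. ESRD**

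If the first eGFR below 15 is on day d, the confirming value cannot come before day d + 21. A subject who starts dialysis and dies before then cannot meet the ESRD definition, although the death counts in the composite. For survivors, the interval has a purpose: 9.1.8 uses it to confirm a sustained change in renal function. Large falls also cross another endpoint. Entry requires eGFR of at least 45, and the protocol's MDRD formula raises creatinine to the power −1.154. A fall from 45 to 15 at unchanged age therefore means creatinine multiplied by (45/15)^(1/1.154) = 3^0.867 ≈ 2.6. That is well past the safety endpoint of a rise above 50%, which carries no 21-day condition in its listing. Section 9.1.8 does require the repeat draw before an adverse event is reported.

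**The case against.** The strongest reply is that little is lost. Every early death is in all-cause mortality and the composite, and a hemorrhagic stroke also appears under TIMI bleeding. Listing stroke as a cause of cardiovascular death shows that fatal strokes were foreseen. A fatal stroke whose deficit lasts beyond 24 hours counts as usual. Subjects with a previous cerebrovascular accident or transient ischemic attack are excluded, and safety is descriptive with no hypothesis. All of this stands, and it makes the point a minor one. It does not put the event into the stroke rate.

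A second reply is that the CEC works under its own charter, which is not among the documents and may say how early deaths are classified. That is possible. The version 5.0 change log says the event definitions were updated to match the charter, so an override there cannot be assumed or ruled out.

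A reader might go further and infer that the 21-day conditions for ESRD and creatinine doubling have the same fault, or that the worst safety events in general go uncounted. The documents do not support that:

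- Creatinine doubling is only one example of embolic end-organ damage. A case that fails it can qualify by another route, such as a kidney infarct, so no override is needed.
- Dialysis after one low eGFR may be reversible acute injury; the protocol itself anticipates contrast nephropathy. Separating that from end-stage disease is what the interval is for.
- Nothing in the documents shows that starting dialysis would prevent a second low eGFR from being recorded.
- Losing one kidney is not by itself end-stage disease, so kidney removal is not a sound reason to waive confirmation.

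**Conclusion.** The point holds for stroke, narrowly. As written, a stroke fatal within 24 hours is outside the stroke endpoint, and no rule in the protocol or SAP brings it back. One such event would move the stroke rate from 1/50 (2%) to 0/50 (0%). This assumes about 50 evaluable treated subjects, literal application of 16.4, and a CEC charter without its own rule for early death. The composite, the mortality count, the efficacy analyses and the sample size are unchanged.

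For ESRD, the only gap worth closing is the subject on dialysis who dies before the confirming sample is due. The two creatinine-doubling intervals, at least 21 days in one place and over 21 days in the other, differ for a sample taken on exactly day 21 and need reconciling. The matter is low priority, but it is cheap to settle before any case occurs.

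**What to change.** - **Stroke (Protocol 16.4).** Extend the condition so that the deficit *persists more than 24 hours or leads to death within 24 hours*. Make the same change in the CEC charter if it uses the same wording.
- **ESRD.** Keep the 21-day confirmation. Add that the CEC classifies a subject on dialysis who dies before the second eGFR can be drawn.
- **Creatinine doubling.** Use one interval wording in both places in 16.4.

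The cost is a few short clauses and no new data. The one downside for the sponsor is that the reported stroke rate may be slightly less favourable.
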